5.2.3 Participant departure from vaccine schedule

If a participant misses a scheduled vaccination, they are eligible for future vaccinations (see Section 5.2.1). The site investigator can petition the PSRT for an out of window vaccination.

5.2.4 Discontinuation of study participation

A participant may be discontinued from protocol participation for the following reasons:

- Participant voluntarily withdraws;
- CRS determines the participant is lost to follow-up;
- The investigational new drug (IND) application sponsor or regulatory authorities stop the study; or,
- PI assessment that it is not in the best interest of the participant to continue participation in the study or that the participant's compliance with the study is not sufficient.

If a participant terminates participation in the study early for any reason, the site PI should consider if the following assessments are appropriate: end-of-study HIV test, complete blood count (CBC with differential, serum chemistry [ALT and creatinine], physical examination, and if indicated, a pregnancy test [see Appendix A and Appendix B]). For participants living with HIV, please see

Section 8.8. If the site PI has questions regarding a termination visit, they should consult with the PSRT.

6 Statistical considerations

This phase-1 study will target recruiting a total of 45 adult participants without HIV aged 18 to 55 years.

In Group 1, a total of approximately 9 participants will receive 3 administrations of sD-NP-GT8 DNA at a dose of 0.4 mg, coformulated with IL-12 DNA at a dose of 0.1 mg at days 1, 29, and 85. Study products will be administered intradermally via EP of the skin on each upper arm.

In Group 2, a total of approximately 18 participants will receive 3 administrations of sD-NP-GT8 DNA at a dose of 1.6 mg, coformulated with IL-12 DNA at a dose of 0.4 mg at days 1, 29, and 85. Study products will be administered intradermally via EP of the skin on each upper arm.

In Group 3, a total of approximately 18 participants will receive 3 administrations of sD-NP-GT8 DNA at a dose of 1.6 mg, coformulated with IL-12 DNA at a dose of 0.4 mg at days 1, 29, and 85. These doses will be administered intradermally via EP of the skin on each upper arm. All participants in Group 3 will also receive 2 administrations of Trimer 4571 at a dose of 100 mcg adjuvanted with 5 mcg of 3M-052-AF + 500 mcg Alum via IM injections into the deltoid muscle at days 85 and 169.

The first 5 participants enrolled in the study will be assigned to Group 1. The PSRT will convene to review safety data recorded from these 5 participants through the visit scheduled 2 weeks post–first vaccination. If the PSRT determines that it is safe to proceed with enrollment, the remaining participants (approximately 40) will be randomized between Groups 1, 2, and 3.

Participants will be monitored for up to 18 months postenrollment. We anticipate that the study will take at least 22 months to be completed.

Participants will be evaluated for safety and immune responses through blood collection, lymph node FNA, and leukapheresis at specified timepoints throughout the study.

The study will target enrolling at least 50% of participants willing to undergo FNA in Groups 2 and 3. Participants enrolled in Group 1 will not undergo FNA. See Sections 1.5 and 2.11 for details.

Primary and secondary objectives will seek to characterize and compare immunogenicity endpoints between treatment groups. Since allocation ratios used to enroll participants may vary between groups during enrollment (eg, participants will be preferentially assigned to Groups 2 and 3 relative to Group 1 after Group 1 has enrolled its first 5 participants), group comparisons will be cautiously interpreted. Moreover, in order to mitigate potential biases, statistical analyses may adjust for potential confounders (eg, age) when comparing endpoints between groups.

6.1 Sample size justification and accrual

The protocol team will convene after the final enrolled participant has completed Visit 6 (first FNA visit) to determine if further participants should be enrolled to ensure adequate samples for immunogenicity analysis. Examples of reasons that might necessitate enrollment of additional participants are provided in Section 1.5. If some participants of the original 45 enrolled will not contribute data to some of the immunogenicity analyses, the protocol team may enroll up to 9 additional fully evaluable participants, or a total of 54 participants enrolled, with the goal of 45 contributing to the final immunogenicity analyses. Participants will not be replaced after completion of visit 6, the first FNA visit.

Every study participant will be followed up for an AESI contact at month 18.

Details about the pace of enrollment can be found in Section 1.5.

Since enrollment is concurrent with receiving the first vaccination, all participants will provide some safety data. However, for immunogenicity analyses, data may be missing for a variety of reasons, including participants terminating from the study early, problems in shipping specimens, or high assay background. Immunogenicity data from 17 phase 1, 2, and phase 2a HVTN vaccine trials, which began enrolling after June 2005 (data as of September 2014), indicate that 17% is a reasonable estimate for the rate of missing data. Therefore, the sample-size calculations in Section 6.1.1 below account for about 17% of enrolled participants having missing data.

6.1.1 Power calculations for immunogenicity

The primary goal of the statistical immunogenicity analyses is to evaluate vaccine-induced immune responses in each treatment group by timepoint. The primary immunogenicity endpoints will be the response rate and magnitude of HIV-1–specific binding Ab responses, as measured by a multiplex assay; the response rate and magnitude of CD4+ and CD8+ T-cell responses to HIV-1– specific Env peptide pools, as measured by flow cytometry; and the frequency of VRC01-class B cells from lymph nodes and periphery following the second and third vaccinations, as measured by B-cell receptor (BCR) sequencing.

The primary and secondary statistical analyses of immunogenicity data will include the following comparisons:

- Group k postbaseline versus Group k at baseline to assess vaccine-induced immune responses within Group k, where k = 1, 2, 3. Groups 2 and 3 may be combined when comparing immune responses measured between baseline and Day 85 and those measured at baseline because participants in these 2 groups will have received the same products until Day 85.
- Group 1 versus Groups 2 and 3 combined to compare immune responses in the low- and high-dose groups (without administration of Trimer 4571) between Day 1 and Day 85.

- Group 1 versus Group 2 to compare immune responses in the low- and high-dose groups (without administration of Trimer 4571) post–Day 85.
- Group 2 versus Group 3 to compare immune responses with and without administration of Trimer 4571 post–Day 85.

[figure not shown]
Response magnitudes may be summarized using sample means and their two-sided 95% confidence intervals (CIs). Response rates will be estimated using empirical proportions; their two-sided 95% CIs will be constructed using the score method described in Agresti and Coull (1998) (53).

Comparisons of response magnitudes between timepoints within individual treatment groups or pooled treatment groups (eg, Groups 2 and 3 postbaseline versus baseline) will be carried out using Wilcoxon signed-rank tests.

Comparisons of response magnitudes between 2 independent groups (eg, Group 2 versus Group 3) within timepoints will be done using Wilcoxon rank-sum tests.

The power achieved by the Wilcoxon rank-sum and the Wilcoxon signed-rank tests was computed as a function of the effect size for various sample sizes: n = 9, 15, 18, 30, 36, 45, including cases when no data are missing and cases when $\sim 17\%$ of the data are missing. These calculations also describe the power achieved by statistical comparisons of data measured in FNA samples if only 50% of participants enrolled in Groups 2 and 3 (ie, n = 9 participants per group or n = 18 in Groups 2 and 3 combined) consent to providing FNA samples. The calculations assumed that observations are normally distributed and that the number of observations in both groups or timepoints is identical.

The power function of the tests under these scenarios is presented in Figure 6-1. For instance, when comparing 2 independent groups of equal sizes n = 15 (eg. Groups 2 or 3 with about 17% loss to follow-up), the study achieves about 80% power to detect a significant difference at the 5% significance level using a twosided Wilcoxon rank-sum test if the average increase in the standardized (Cohen's) effect size is about 1.1. For example, if the proportion of VRC01-class B cells two weeks after the second vaccination was 1.0% in Group 1 and 2.1% in Group 2, with a standard deviation of about 1.0% in both groups, the standardized effect size would be 1.1 = (2.1%-1.0%)/1.0%, and the study would have approximately 80% to detect a significant difference between the two groups using a two-sided Wilcoxon rank-sum test at the 5% significance level. With a sample size of n = 18 per group (eg, Groups 2 or 3 with no loss to follow-up), the test has about 80% power to detect a significant difference if the standardized effect size is 1.0. Thus, if the proportion of VRC01-class B cells two weeks after the second vaccination was 1.0% in Group 1 and 2.0% in Group 2, with a standard deviation of about 1.0% in both groups, the standardized effect size would be 1.0 = (2.0%-1.0%)/1.0%, and the study would have approximately 80% to detect a significant difference between the two groups using a two-sided Wilcoxon rank-sum test at the 5% significance level.

[figure not shown]

Figure 6-1 Left panel: Power of a two-sided Wilcoxon rank-sum test comparing 2 independent groups. Right panel: Power of a two-sided Wilcoxon signed-rank test comparing 2 groups of paired observations (eg, the frequency of VRC01-class B cells postvaccination and at baseline within a single group). The power was calculated as a function of (1) the standardized effect size, defined as the average difference between the 2 group means divided by the common group standard deviation (left-hand side) or as the mean difference divided by the standard deviation of the difference (right-hand side) and (2) the sample size (n = 9, 15, 18, 30, 36, and 45).

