6.4.2 Immunogenicity analyses

For the statistical analysis of immunogenicity endpoints, data from enrolled participants will be used according to the initial randomization assignment, regardless of how many injections each participant received. Additional analyses may be performed, limited to participants who received all scheduled injections per protocol. Assay results that are unreliable, or are from participants living with HIV postdiagnosis, are excluded. Since the exact date of HIV acquisition is unknown, any assay data from blood draws 4 weeks prior to a participant living with HIV's last seronegative sample and thereafter may be excluded. If a participant living with HIV does not have a seronegative sample postenrollment, then all data from that participant may be excluded from the analysis.

The goals of the primary and secondary immunogenicity analyses, including group comparisons, are presented in Section 3.

Discrete categorical immunogenicity endpoints (eg, response rates) will be analyzed by tabulating the frequency of positive response by timepoint and treatment group. Crude response rates will be presented with their corresponding 95% CI estimated based on the score test method (42). Barnard's exact tests may be employed to compare the response rates of certain immune responses between 2 treatment groups.

Quantitative assay endpoints (eg, frequencies of CD4-bs B cells as measured by flow cytometry) will be summarized by timepoint within treatment groups by tabulating univariate summary statistics (eg, mean, median, standard deviation, range) and plotting observations using boxplots. Comparisons of continuous outcome variables measured in 2 independent groups will be performed using the Wilcoxon rank-sum test. Comparisons of paired continuous outcome variables measured in 1 group will be performed using the Wilcoxon signed-rank test.

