- ⁴ Contraception status assessment is required only for participants who were assigned female sex at birth and are capable of becoming pregnant. Participants will also be provided with counselling about contraception.
- ⁵ Risk-reduction counseling per CRS Standard Operating Procedures (SOP).
- ⁶ Concomitant medications, including prescription and nonprescription drugs, vitamins, topical products, alternative/complementary medicines, recreational drugs, vaccinations, and allergy shots, are recorded during screening, at enrollment, and at each subsequent clinic visit.
- ⁷ During concomitant medications check-in participant is counseled to avoid medications that would increase the risk of bleeding for 7 days prior to FNA (see Section 8.5).
- ⁸ Vaccination (in-clinic assessments): At least 60 minutes after the first vaccination and after the fourth vaccination, and 30 minutes after for all other vaccinations. Prior to clinic discharge, the injection site and systemic symptoms will be assessed, and participants will have vital signs taken.
- 9 Reactogenicity: Clinic staff will follow new or unresolved reactogenicity symptoms present at the final reactogenicity day (see Section 8.3 and HVTN 305 SSP)
- 10 Pregnancy test: For participants assigned female sex at birth. Pregnancy test may be performed on blood specimens. Persons who are NOT capable of becoming pregnant due to total hysterectomy or bilateral oophorectomy (verified by medical records) or menopause (no menses for ≥ 1 year) are not required to undergo pregnancy testing. For persons who are confirmed pregnant, pregnancy testing is not required unless clinically indicated.
- ¹¹ Local labs may assign appropriate alternative tube types for locally performed tests.
- ¹² HIV screening test: See Section 5.1.1.
- ¹³ **Research samples:** Blood-draw volumes for each tube type shown. Alternate tube types may be used under certain conditions (eg, product shortages) upon approval of the HVTN Laboratory Center. Refer to the Specimen Collection SSP for more information.
- ¹⁴ Blood draw will be performed before vaccination.
- ¹⁵ **Leukapheresis:** May be performed prior to enrollment visit once the participant has been found to have met all protocol enrollment criteria (see Section 5.1.1 and 5.1.2) and leukapheresis eligibility criteria (see Section 8.6).
- ¹⁶ Fine Needle Aspiration: Target for FNA is 3 weeks post–second and –third vaccinations.

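### The post-Day 85 Group 2 v Group 3 magnitude tests leave out the pre-boost response; a rank ANCOVA on it would gain power when that response predicts the outcome and cost almost nothing when it does not

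*Protocol*

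**What the plan says.** Protocol Section 6.1.1 lists four comparisons. The last is "Group 2 versus Group 3 to compare immune responses with and without administration of Trimer 4571 post–Day 85". For magnitudes the method is "Comparisons of response magnitudes between 2 independent groups (eg, Group 2 versus Group 3) within timepoints will be done using Wilcoxon rank-sum tests". Section 6.4.2 repeats it: "Comparisons of continuous outcome variables measured in 2 independent groups will be performed using the Wilcoxon rank-sum test". Neither section brings in a pre-boost value.

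Section 6.1.1 also allows Groups 2 and 3 to be pooled for earlier timepoints, on the ground that "participants in these 2 groups will have received the same products until Day 85".

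Appendices A and B schedule these samples before the first Trimer dose:
- Visit 5 (Day 43): 34 mL serum and 136 mL blood for PBMC.
- Visit 7 (Day 85): 136 mL blood for PBMC, with the footnote "Blood draw will be performed before vaccination". No serum is drawn at this visit.
- Visit 6 (Day 50): a lymph-node aspirate, in participants who opted for FNA.

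The only adjustment wording is in the introduction to Protocol Section 6, repeated in SAP Section 5. It permits, but does not require, adjustment for potential confounders. It gives age as the example, and its stated purpose is to reduce bias. The SAP supplied covers safety and tolerability and contains no immunogenicity model.

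**The concern.** Participants differ in how strongly they respond to the DNA prime. Where that carries through to the post-boost value, it adds noise to the Group 2 v Group 3 comparison, and the trial already samples it. Both groups are allocated by block randomization and have had the same two DNA doses at that point, so a pre-boost value works as a baseline covariate for the Trimer contrast. Adjusting for it introduces no bias from treatment.

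The contrast matters. Protocol Section 2.6 gives the comparison of DNA plus protein with DNA alone as a reason for the design. It is also the one between-group contrast in which every participant is randomized, because the first five Group 1 participants are assigned directly. Groups are small: 18 each, about 15 after the allowed missing data, and about 9 each for lymph-node endpoints if half consent to FNA.

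**Working it through.** **Inputs from the Protocol.** Two-sided 5% test, normal data and equal groups (Section 6.1.1). Missing data 17% (Section 6.1): 18 × 0.83 = 14.9, so about 15 per group. FNA subset 9 per group (Section 6.1.1). **Not in the documents:** the correlation r between the pre-boost and post-boost value of the same assay. It is varied here from 0 to 0.7.

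**Step 1: reproduce the plan's power.** At 15 per group the Protocol claims about 80% power "at the 5% significance level using a twosided Wilcoxon rank-sum test if the average increase in the standardized (Cohen's) effect size is about 1.1". At 18 per group, "the test has about 80% power to detect a significant difference if the standardized effect size is 1.0". Simulating the rank-sum test on normal data with SD 1 gives 80.0% (exact p-values) and 79.9% (asymptotic) for the first, and 80.6% and 80.0% for the second. Both claims reproduce.

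**Step 2: add the covariate.** Let x be the pre-boost value and y = r·x + √(1 − r²)·e + d·g, where x and e are independent standard normal, g is 0 for Group 2 and 1 for Group 3, and d is the difference in SD units. Quade's rank ANCOVA ranks x and y over both groups together, regresses rank(y) on rank(x), and compares the residuals between groups.

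| Setting | Rank-sum | Quade, r = 0 | r = 0.3 | r = 0.5 | r = 0.7 |
|---|---|---|---|---|---|
| 15 per group, d = 1.1 | about 80% | about 80% | 83% | 88% | 96% |
| 18 per group, d = 1.0 | about 80% | 80% | 83% | 89% | 96% |
| 9 per group, d = 1.1 | about 53% | 55% | 58% | 65% | 77% |

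Simulation error is about a point. The small difference at r = 0 with 9 per group carries no covariate information. The rank-sum test is slightly conservative at that size.

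**Step 3: type I error.** With d = 0 and 15 per group, Quade's test rejects in 4.9% to 5.3% of runs. It stays near 5% with 9 per group, and with half to 80% of covariate values tied at an assay floor.

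**Step 4: detectable effect.** For linear ANCOVA on normal data the residual SD shrinks by √(1 − r²). With 15 per group, the difference detectable with 80% power is about 1.08 at r = 0. It becomes 1.08 × √0.91 = 1.03 at r = 0.3, 1.08 × √0.75 = 0.94 at r = 0.5, and 1.08 × √0.51 = 0.77 at r = 0.7. The plan's figure is 1.1.

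**Step 5: covariate at an assay floor.** 15 per group, d = 1.1, r being the correlation before flooring. With half the covariate values at the floor, Quade gives about 82%, 87% and 93% at r = 0.3, 0.5 and 0.7. At r = 0.5, it gives about 84% with 80% at the floor and 82% to 83% with 90% at the floor. The gain fades, but power does not fall below that of the rank-sum test.

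**Step 6: why not a change score.** A rank-sum test on post minus pre, 15 per group and d = 1.1, has power 50%, 65%, 80% and 95% at r = 0, 0.3, 0.5 and 0.7. It loses badly when r is low.

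**The case against.** A reader might infer that the planned test is wrong, or that power is thrown away for no reason. The documents do not support that. The rank-sum test is valid, suits small and possibly skewed samples, and is the test the power calculation uses. Nor do they rank this contrast as the key one: Section 6.1.1 puts evaluation of responses within each group by timepoint first, and Group 2 v Group 3 is one of four unranked comparisons. It also cannot be said that adjustment is excluded, since optional adjustment is allowed and no immunogenicity SAP was supplied.

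The stronger objections concern size and fit, and they largely stand:
- **r is undocumented.** At r = 0 there is no gain. Trimer-specific antibody, a named primary readout, may be near the assay floor after two GT8 DNA doses (an assumption), because Trimer is first given on Day 85.
- **The covariate precedes the full DNA course.** It follows two of three doses, the third being given with the first Trimer dose. The last pre-boost serum is Day 43, which is 183 − 43 = 140 days before the post-fourth-vaccination sample.
- **Rare peripheral B cells.** Section 2.12 says ordinary blood volumes yield too few cells, and leukapheresis is done only at screening and after dose 3. On its figures, 136 mL × 1 million PBMC/mL ÷ 20 million is about 7 precursor cells at the quoted precursor frequency. Vaccination may raise this, but the covariate would still be noisy.
- **FNA.** Section 8.5 does not require Visits 6 and 9 to sample the same node or side, so their correlation is unknown.
- **Scope.** Response rates are untouched, and some pre-boost assays are not listed endpoints. Section 3.2 frames the Day 43 eOD-GT8 antibody readout for Groups 1 and 2.

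These points call for an endpoint-specific rule. They do not remove the case for one, because adjustment costs almost nothing when r is zero. The optional confounder clause does not fill the gap either: it names no pre-boost value and leaves the choice of covariate open after the data are seen.

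**Conclusion.** The point holds as an efficiency refinement and not as an error in the plan. At the plan's own 15 per group and 1.1 SD, using the pre-boost response adds nothing at r = 0, about 3 points of power at r = 0.3, 8 at r = 0.5 and 16 at r = 0.7. With 9 per group, r = 0.5 adds about 12 points and r = 0.7 about 24. These figures assume normal data, equal groups and an r that the documents do not supply. Floors in the covariate shrink the gain, possibly to nothing for Trimer-specific readouts. Because the downside is negligible and the method remains rank-based, it is worth adopting wherever a usable pre-boost value exists.

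**What to change.** In Protocol Sections 6.1.1 and 6.4.2, or in an immunogenicity SAP finalized before the data are examined, pre-specify Quade's rank ANCOVA for Group 2 v Group 3 magnitude endpoints after Day 85. The covariate is the same assay's last pre-boost value, wherever that assay is run before the boost:
- **Lymph-node endpoints at Visit 9:** the Visit 6 aspirate.
- **Binding antibody:** Visit 5 serum.
- **T cells:** Visit 5 PBMC or the pre-vaccination Visit 7 PBMC, with the choice stated in advance.
- **Rare peripheral VRC01-class B cells:** do not rely on Visit 7 PBMC; keep the rank-sum test as the main analysis.

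Fill a missing covariate with the pooled Group 2 and 3 mean, so that nobody is dropped. Keep the rank-sum test as a sensitivity analysis, and as the main test where no usable pre-boost value exists. Do not use a raw change score.

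Cost: analysis-plan wording, one degree of freedom, and possibly added assay runs on stored samples, for example Group 3 antibody at Day 43 or T cells at Day 43 or Day 85. No new visit or blood draw is needed.

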8.1 Screening

Screening for eligibility will be performed after informed consent has been obtained and properly documented before enrollment. Screening evaluations and sample collection include medical history review, physical exam, and any clinical laboratory tests, as detailed in the schedule of procedures (Appendix A and Appendix B), needed to confirm eligibility. Persons assigned female sex at birth who are of reproductive potential will be given a pregnancy test. Additional assessments of health may be conducted at screening based on clinical judgment.

An AoU will be completed prior to enrollment. Records will be kept documenting the reason that screened participants did not enroll.

Leukapheresis specimens for baseline comparison will be drawn during the screening period if a participant meets all additional eligibility criteria and wishes to join the study (Sections 5.1.1 and 8.6).

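### Between-group tests of response magnitude make no use of the baseline value that every participant provides; naming a baseline-adjusted rank test would cost almost nothing

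*Protocol*

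**What the plan says.** Protocol Section 6.1.1 states that comparisons of magnitude between two independent groups "within timepoints will be done using Wilcoxon rank-sum tests". Section 6.4.2 repeats the choice: "Comparisons of continuous outcome variables measured in 2 independent groups will be performed using the Wilcoxon rank-sum test". Neither sentence has a baseline term. The planned contrasts are Group 1 against Groups 2 and 3 pooled up to Day 85, then Group 1 against Group 2 and Group 2 against Group 3 after Day 85.

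A baseline value is available for the blood endpoints. Section 8.1 says "Leukapheresis specimens for baseline comparison will be drawn during the screening period", Section 2.12 plans leukapheresis for all participants, and Appendices A and B schedule 34 mL of serum at screening. Section 6.1.1 uses the baseline within each group, comparing post-baseline with baseline values by the Wilcoxon signed-rank test.

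Protocol Section 6 and SAP Section 5 allow, without requiring, adjustment of group comparisons for possible confounders. Age is the only example given, and no method is named. The supplied SAP covers safety and tolerability and does not set the immunogenicity tests.

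**The concern.** Groups are small (9, 18 and 18). When the baseline predicts the later response, a comparison of later values alone carries between-person variation that the baseline could have removed. The trial pays for the baseline leukapheresis and serum in any case.

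There is a second reason in the Group 1 comparisons. The first 5 participants are assigned to Group 1, and randomization covers only the remaining 40 or so (4, 18 and 18). Any baseline difference between those 5 and later enrollees passes into an unadjusted comparison in proportion to the baseline-outcome correlation.

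The optional adjustment wording does not settle this. A rank-sum test cannot carry a covariate, and the choice of covariate and method stays open in an open-label trial.

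**Working it through.** **Inputs from the protocol (Section 6.1.1).** Two-sided 5% rank-sum test and normal data. One case is "when comparing 2 independent groups of equal sizes n = 15" with an effect of about 1.1 SD; the other has 18 per group and an effect of 1.0 SD. The stated power is about 80% in both.

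**Input not in the documents.** The correlation ρ between baseline and later response is an assumption, varied from 0 to 0.7.

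**Step 1: reproduce the plan's figure.** Simulated rank-sum power (20,000 replicates) is 79.5% at 15 v 15 and 1.1 SD, and 80.2% at 18 v 18 and 1.0 SD. Both agree with the protocol.

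**Step 2: what adjustment can yield in principle.** Linear adjustment turns the effect d into d/√(1−ρ²), which is equivalent to multiplying the sample size by 1/(1−ρ²). For d = 1.1:
- ρ = 0.3: 1.1/√0.91 = 1.15; multiplier 1/0.91 = 1.10
- ρ = 0.5: 1.1/√0.75 = 1.27; multiplier 1/0.75 = 1.33
- ρ = 0.7: 1.1/√0.51 = 1.54; multiplier 1/0.51 = 1.96

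**Step 3: simulated power.** Quade's method ranks baseline and outcome across both groups, regresses outcome ranks on baseline ranks, and compares the residuals between groups. Bivariate normal data, 10,000 replicates per cell:

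| Case | Test | ρ = 0 | 0.3 | 0.5 | 0.7 |
|---|---|---|---|---|---|
| 15 v 15, 1.1 SD | Rank-sum | 79.8% | 79.2% | 79.8% | 79.9% |
| 15 v 15, 1.1 SD | Quade | 79.7% | 82.0% | 88.0% | 96.0% |
| 15 v 15, 1.1 SD | Rank-sum on change | 49.9% | 65.2% | 79.3% | 95.3% |
| 18 v 18, 1.0 SD | Rank-sum | 80.6% | 80.9% | 80.9% | 80.6% |
| 18 v 18, 1.0 SD | Quade | 80.1% | 83.3% | 88.9% | 96.2% |

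With no true difference at 15 v 15, the rank-sum test rejects in 4.1 to 4.7% of replicates and Quade in 4.8 to 5.2%. Both hold their level. The change score loses badly at low ρ and gains on the plain test only when ρ exceeds about 0.5.

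**Step 4: Group 1 comparisons (1.1 SD).** At 9 v 18 (Group 1 v Group 2, nothing missing), rank-sum power of about 69% becomes about 72%, 79% and 91% with Quade at ρ = 0.3, 0.5 and 0.7. At 9 v 30, about 77% becomes about 80%, 86% and 95%.

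**Step 5: baselines at the assay floor (15 v 15, 1.1 SD).** With 80% of baselines at the floor, power goes from 81% to 82% at an underlying ρ of 0.3, and from about 80% to 83–84% at 0.5. With 90% at the floor, it goes from 80% to 80% and from 80% to 83%. With all at the floor, Quade gives 80% and the rank-sum test 79%, so nothing is lost. A stronger underlying correlation would give somewhat more.

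**Step 6: bias from the 5 non-randomized participants.** Suppose their baseline differs by 1 SD (an assumption). The Group 1 mean baseline then shifts by 5/9 = 0.56 SD, of which 0.56 × 0.5 = 0.28 SD reaches the outcome at ρ = 0.5 and 0.56 × 0.7 = 0.39 SD at ρ = 0.7. At 9 v 18 with no vaccine difference, the rank-sum test rejects in about 8.5% and 12% of simulations; Quade stays at 4 to 5%. With a 0.5 SD shift the inflation is small, at 5 to 6%.

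**The case against.** **The plan already allows adjustment.** Section 6 follows its remark on unequal allocation with a promise of cautious interpretation and the option to adjust, and age is only an example. A reader might infer that the plan rules out adjustment; it does not. What remains is that the option names neither the baseline response nor a method.

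**Baseline is not thrown away.** A reader might infer that the baseline samples go unused. That is wrong: they are central to the within-group tests, which serve the stated primary aim of assessing vaccine-induced responses in each group. The gap is confined to the between-group tests.

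**The planned test is sound.** A reader might infer that the rank-sum comparisons are invalid. Among randomized participants they are valid, and the stated power is right. For Group 2 v Group 3, where all 36 are randomized, there is no bias argument.

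**Baselines may be uninformative.** Participants are HIV-negative and have not received an investigational HIV vaccine, and Section 2.12 puts precursor B cells at about 1 in 20 million cells. Floor-level baselines are plausible for several endpoints, so the 88% and 96% figures should not be read as expected gains. This objection stands in full on size. It does not argue against the change, because adjustment then costs essentially nothing.

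**The immunogenicity SAP was not supplied.** Baseline adjustment might be specified there; that cannot be judged from these documents.

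**Conclusion.** The point holds as a low-cost improvement and not as an error. The named between-group tests leave out a baseline value that is collected from every participant, and no text in the supplied documents commits to using it.

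For Group 2 v Group 3 the loss is efficiency only. For Group 1 comparisons, adjustment also protects against baseline imbalance from the 5 assigned participants, but only the part that the measured baseline captures.

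The size rests on an assumed correlation and on normal data. Starting from about 80% power at 15 v 15 and 1.1 SD, the gain is about 2 points at a correlation of 0.3, 8 at 0.5 and 16 at 0.7. It falls to about 0 to 5 points if most baselines are at the floor and the underlying correlation is 0.3 to 0.5. The bias figures also rest on an assumed 1 SD shift, for which the documents give no evidence either way.

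**What to change.** In Protocol Sections 6.1.1 and 6.4.2 and in the immunogenicity SAP:

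- Pre-specify rank analysis of covariance (Quade) on the baseline value as the governing between-group test for quantitative blood endpoints that have a baseline sample.
- Report the unadjusted rank-sum test as a supporting analysis, so that the choice between two p-values is settled in advance.
- Keep participants whose baseline is missing by a simple pre-stated rule, for example by assigning the mid-rank. Section 6.1 expects about 17% missing immunogenicity data, so a rule is needed.
- Use the rank-sum test alone for FNA endpoints, which are sampled only after the second and third doses.
- Do not make change from baseline the default.

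The cost is a few lines of text and slightly more analysis work. No new samples, visits or participants are needed.
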